3.1.3 Data Monitoring Committee

The monitoring of the safety and tolerability of CyPep-1 + pembrolizumab will be performed by the DMC.

This will include all the patients in the Phase 1b portion and thereafter, all patients who have entered the study. This will be conducted on a regular basis, as defined in the DMC charter.

After the DMC reviews the safety data, feedback will be provided to the Sponsor regarding the further conduct of the study. The DMC will be comprised of independent members or designees. The DMC will strive for a consensus opinion regarding the data reviewed.

At the end of each DMC review meeting, the DMC will provide 1 of the following feedback to the Sponsor:

- The study is proceeding in line with the study protocol; or
- The study is not proceeding in line with the study protocol and/or there is a possible change in the benefit/risk ratio.

The observation of any Discontinuation of Enrollment Criteria (Section 4.5.3) for Phase 2a patients must trigger the immediate decision by the Sponsor to stop recruitment and organize an urgent DMC meeting, which will assess the causality of the observed AEs and the fulfillment of the criteria. The DMC will formulate a recommendation to resume recruitment, discontinue the involved cohort, or stop the study.

The Sponsor will act upon the feedback as appropriate, ie, the final decision will be made by the Sponsor. The Sponsor or designee will notify the study team (ie, the responsible project manager) of the final decision regarding the DMC feedback, including any actions to be taken. The Sponsor or designee will communicate the DMC feedback and/or final decision of the Sponsor to all

Investigators and the Institutional Review Board (IRB)/Independent Ethics Committee (IEC), if applicable.

3.1.4 Coronavirus Disease 2019 Contingency Measures

In cases of COVID-19 limitations, it is the Investigator's responsibility to assure the safety of patients via phone or video contact to assess the patient's well-being and assess for any AEs and collect additional clinical data as best as possible. Where available and appropriate, home health care may be considered to facilitate monitoring of safety and study continuity. Documentation of these cases and the study site's management of patients should be recorded in the Investigator study files. The impacts of the COVID-19 pandemic on the outcomes of this study, including any protocol deviations that result from COVID-19 illness and/or COVID-19 control measures, will be discussed in the CSR. In the absence of a COVID-19 impact, it is expected that Investigators and patients follow the protocol requirements as set forth.

3.2 Study Indications

The indications of this study are advanced or metastatic HNSCC, melanoma, or TNBC.

4 SELECTION AND WITHDRAWAL OF PATIENTS

4.1 Inclusion Criteria

No waivers for inclusion or exclusion criteria will be given.

4.1.1 General Inclusion Criteria

Patients who meet all of the following criteria will be eligible to participate in the study:

- 1. Are 18 years of age or older on the day of signing informed consent;
- 2. Provide written informed consent and are able to comply with study procedures and assessments;
- 3. Have measurable disease per RECIST v1.1 as assessed by the local site Investigator/radiology. Lesions situated in a previously irradiated area are considered measurable if progression has been demonstrated in such lesions;
- 4. Have at least 1 non-ulcerated, measurable, and accessible lesion for IT injection with a maximum diameter of 5 cm;
- 5. Are able to provide tissue from a core or excisional biopsy at screening or have an acceptable stored tumor sample available that was collected within 90 days prior to screening;
- 6. Have an Eastern Cooperative Oncology Group (ECOG) performance status of 0 or 1 (Appendix C);
- 7. Have a life expectancy \geq 3 months, as determined by the Investigator;
- 8. Female patients of non-childbearing potential must be either surgically sterile (hysterectomy, bilateral tubal ligation, salpingectomy, and/or bilateral oophorectomy at least 26 weeks before screening), post-menopausal, defined as spontaneous amenorrhea for at least 2 years, or with follicle-stimulating hormone in the post-menopausal range at screening;
- 9. Female patients of childbearing potential (defined as <2 years after last menstruation or not surgically sterile) must have a negative serum pregnancy test at screening and agree to use a highly effective method for contraception from the time of signing the ICF until at least 120 days after the last administration of study treatment. Highly effective methods of contraception are birth control methods with a failure rate of <1% per year when used consistently and correctly, including the following:
 - O Combined estrogen- and progestin-containing hormonal contraception associated with inhibition of ovulation given orally, intravaginally, or transdermally; progestin-only hormonal contraception associated with inhibition of ovulation given orally, by injection, or by implant; intrauterine devices; and intrauterine hormone-releasing systems;
 - Female sterilization (surgical bilateral oophorectomy with/without hysterectomy, total hysterectomy, bilateral tubal occlusion/ligation) at least 26 weeks prior to first study treatment;
 - o Sterilization of male partner (at least 6 months prior to first study treatment dose); and
 - o Complete sexual abstinence. Periodic abstinence (eg, calendar) and withdrawal are not acceptable. Sexual abstinence is considered a highly effective method only if defined as

refraining from heterosexual intercourse during the entire period of risk associated with the study treatment. The reliability of sexual abstinence needs to be evaluated in relation to the duration of the study and the preferred and usual lifestyle of the patient.

- 10. Male patients able to father children must agree to use 2 acceptable methods of contraception throughout the study (eg, condom plus spermicidal gel). Sperm donation is not recommended from the time of signing the ICF until at least 120 days after the last administration of study treatment; and
- 11. Have adequate organ function as defined in Table 7. Specimens must be collected within 72 hours prior to the start of study treatment at Cycle 1 Visit 1.

Table 7. Adequate Organ Function Laboratory Values

System	Laboratory Value
Hematological	
ANC	≥1500/µL
Platelets	≥100,000/µL
Hemoglobin ¹	≥9.0 g/dL or ≥5.6 mmol/L
Renal	•
Creatinine OR	≤1.5 × ULN OR
Measured or calculated CrCl ² (GFR can also be used	≥30 mL/min for patients with creatinine levels
in place of creatinine or CrCl)	>1.5 × institutional ULN
Hepatic	
	≤1.5 × ULN OR direct bilirubin ≤ULN for
Total bilirubin	patients with total bilirubin levels >1.5 × ULN
	\leq 2.5 × ULN (\leq 5 × ULN for patients with liver
AST (SGOT) and ALT (SGPT)	metastases)

This table includes eligibility-defining laboratory value requirements for treatment.

ALT (SGPT) = alanine aminotransferase (serum glutamic pyruvic transaminase); ANC = absolute neutrophil count; AST (SGOT) = aspartate aminotransferase (serum glutamic oxaloacetic transaminase); CrCl = creatinine clearance; GFR = glomerular filtration rate; pRBC = packed red blood cell; ULN = upper limit of normal.

4.1.2 Inclusion Criteria for Arm A

Patients who meet all of the general Inclusion Criteria (Section 4.1.1) and the following additional criteria will be eligible for inclusion in Arm A:

- 1. Have histologically confirmed diagnosis of HNSCC (including nasopharyngeal squamous cell carcinoma);
- 2. Have advanced or metastatic HNSCC incurable by standard of care therapies; and
- 3. Have recurrent or metastatic HNSCC that has progressed on or failed both platinum-based chemotherapy AND an ICI (given either sequentially or concurrently).

Note: Patients who received platinum-based chemotherapy with concurrent radiation for locally advanced HNSCC and experienced disease progression within 6 months may also be considered as having disease progression on platinum-based chemotherapy.

^{1.} Criteria must be met without pRBC transfusion within the prior 2 weeks. Patients can be on a stable dose of erythropoietin (approximately ≥3 months).

^{2.} CrCl should be calculated per institutional standard.

4.1.3 Inclusion Criteria for Arm B

Patients who meet all of the general Inclusion Criteria (Section 4.1.1) and the following additional criteria will be eligible for inclusion in Arm B:

- 1. Have histologically confirmed diagnosis of malignant melanoma;
- 2. Do not have uveal melanoma;
- 3. Have advanced or metastatic melanoma incurable by standard of care therapies;
- 4. Have received a combination of a BRAF inhibitor and a MEK inhibitor if diagnosed with a BRAF-mutated melanoma and if clinically indicated; and
- 5. Have failed or progressed on or after treatment with a checkpoint inhibitor administered either as monotherapy or in combination with other checkpoint inhibitors or other therapies.

4.1.4 Inclusion Criteria for Arm C

Patients who meet all of the general Inclusion Criteria (Section 4.1.1) and the following additional criteria will be eligible for inclusion in Arm C:

- 1. Have histologically confirmed diagnosis of TNBC as per ASCO/CAP guidelines;²⁴
- 2. Have advanced or metastatic TNBC incurable by standard of care therapies;
- 3. Have received sacituzumab govitecan chemotherapeutic treatment if clinically indicated; and
- 4. Have failed or progressed on or after treatment with a checkpoint inhibitor administered either as monotherapy or in combination with other therapies (if ICI eligible based on PD-L1 status) OR have received prior systemic therapy with either an anthracycline- or taxane-containing regimen (if ICI non-eligible based on PD-L1 status).

4.2 Exclusion Criteria

Patients who meet any of the following criteria will be excluded from participation in the study:

- 1. Have only non-palpable cutaneous infiltrations (eg, breast cancer cutaneous carcinomatosis);
- 2. Have had anti-cancer therapy within 4 weeks prior to the first dose of study treatment (2 weeks for palliative radiotherapy);

Note: Patients must have recovered from all AEs due to previous therapies to ≤Grade 1 or baseline (alopecia is an allowable exception). Upon discussion with the Sponsor, patients with ≤Grade 2 neuropathy or endocrine-related AEs requiring treatment or hormone replacement may be eligible.

Note: If the patient had major surgery, the patient must have recovered adequately from the procedure and/or any complications from the surgery prior to starting study intervention.

3. Have participated in a clinical trial and received an investigational therapy within 30 days prior to the first dose of study treatment;

4. Have received or will receive a live or live attenuated vaccine within 30 days prior to the first dose of study treatment;

Note: Seasonal flu vaccines that do not contain live vaccine are permitted. COVID-19 vaccines are only permitted with documentation of the date of the vaccine if the last dose of vaccine was administered >14 days prior to the first dose of study treatment. The COVID-19 booster vaccine must be administered at least 14 days prior to the first dose of study treatment and is not allowed during the first 3 months of the Treatment Period.

- 5. Have tested positive for SARS-CoV-2 infection within 14 days prior to the Screening Visit; Note: Patients who have had a known SARS-CoV-2 infection >14 days prior to the Screening Visit are permitted at Investigator discretion and must present with no symptoms.
- 6. Have had a major surgical procedure within 14 days prior to the first dose of study treatment;
- 7. Are expected to require a systemic or localized anti-neoplastic therapy during participation in this study, excluding localized palliative radiotherapy to tumors not selected for evaluation of treatment response;

Note: Use of denosumab for patients with bone metastasis is allowed.

- 8. Are pregnant or breastfeeding;
- 9. Have clinical evidence of a secondary malignancy actively progressing or requiring active treatment other than curative therapies for early stage (carcinoma in situ or Stage 1) carcinomas or non-melanoma skin cancer;
- 10. Have had any autoimmune disease requiring immunosuppressive therapy (ie, use of disease modifying agents, corticosteroids, or immunosuppressive drugs) within 2 years prior to the first dose of study treatment;
 - Note: Replacement therapy (eg, thyroxine, insulin, or physiologic corticosteroid replacement therapy for adrenal or pituitary insufficiency) is not considered a form of systemic treatment and is allowed.
- 11. Have a condition requiring continuous systemic treatment with either corticosteroids (>10 mg daily prednisone equivalent) or other immunosuppressive agents within 2 weeks prior to the first dose of study treatment. Inhaled, intranasal, or topical (only on areas outside the injected lesion[s]) and physiological replacement doses of up to 10 mg daily prednisone equivalent are permitted in the absence of active autoimmune disease;
- 12. Have abnormal or clinically significant coagulation parameters as determined by the Investigator (eg, prothrombin time [PT], international normalized ratio [INR], activated partial thromboplastin time [aPTT]) unless patients are on anti-coagulants in which case it must be within appropriate clinical levels;
 - Note: Patients who are on anti-coagulants must be able to switch to a low molecular weight heparin or equivalent prior to Cycle 1 Day 1 and continue during the Treatment Period.
- 13. Have a significant history or clinical manifestation of any allergic disorders and/or Quincke's edema (as determined by the Investigator) capable of significantly altering the absorption of drugs, of constituting a risk when taking CyPep-1 or pembrolizumab, or of interfering with the interpretation of the data;

- 14. Have a known hypersensitivity to any component of CyPep-1 or pembrolizumab;
- 15. Have a history of adverse reactions from treatment with ICIs, including pembrolizumab, which resulted in discontinuation of ICI or pembrolizumab or has ongoing pembrolizumab-related toxicity event(s) as per treatment-limiting toxicity definitions, except patients with ongoing endocrine disorders that are managed with replacement therapy (ie, hypothyroidism related to prior pembrolizumab treatment);
- 16. Have an active infection requiring systemic therapy;
- 17. Have a known history of Hepatitis B (defined as Hepatitis B surface antigen reactive) or known active Hepatitis C virus (defined as Hepatitis C virus RNA [qualitative] is detected) infection;
 - Note: No testing for Hepatitis B and Hepatitis C is required unless mandated by a local health authority.
- 18. Have had radiotherapy within 2 weeks prior to the first dose of study treatment, are in recovery from radiation toxicity, or have had radiation pneumonitis;
- 19. Have a history of non-infectious pneumonitis/interstitial lung disease that required steroids or has current pneumonitis/interstitial lung disease;
- 20. Have had a prior allogeneic tissue/solid organ transplant, stem cell, or bone marrow transplant;
- 21. Have active human immunodeficiency virus (HIV). Patients are eligible when on stable anti-retroviral therapy (no change in medication or dose) for at least 4 weeks prior to screening, have confirmed virologic suppression with HIV RNA less than 50 copies/mL or the lower limit of quantification (below the limit of detection) using the locally available assay at the time of screening and for at least 12 weeks prior to screening, and have a CD4+ T cell count >350 cells/mm³ at screening. HIV-infected patients with a history of Kaposi sarcoma and/or Multicentric Castleman Disease will be excluded;
- 22. Have 4 or more sites involved, including the primary cancer;
 - Note: A site is defined as an organ (eg, lung, liver, or brain) or a system (eg, lymphatic or central nervous system [CNS]).
- 23. Have a CNS metastasis that is symptomatic, progressing, or that requires current therapy (eg, evidence of new or enlarging CNS metastasis, carcinomatous meningitis, or new neurological symptoms attributable to CNS metastasis);
- 24. Have a QTcF >480 ms at screening, history of long or short QT syndrome, Brugada syndrome, QTc prolongation, or Torsade de Pointes, with the exception of patients with controlled atrial fibrillation, pacemaker, or bundle branch block as the QTc will be prolonged due to the widened QRS;
- 25. Are an adult under legal protection, are vulnerable, or lack the capacity to give informed consent, such as:
 - o Persons deprived of liberty by a judicial or administrative decision;
 - o Adult persons subject to a legal protection measure (under supervision/under guardianship); or
 - o Persons under a judicial protection measure; or

26. Have a history of or current evidence of any condition, therapy, or laboratory abnormality that might confound the results of the study, interfere with the patient's participation for the full duration of the study, or make participation in the study not in the best interest of the patient, in the opinion of the Investigator.

4.3 Retesting

If laboratory abnormalities during screening are considered by the Investigator to be transient, then the laboratory tests may be repeated once during screening. The Investigator's rationale for retesting should be documented. If the retest result is no longer exclusionary, the patient may be enrolled in the study.

4.4 Rescreening

A patient who is screened and does not meet the study eligibility criteria may be considered for rescreening upon Sponsor and/or Medical Monitor consultation and approval. Rescreened patients will keep the original patient identification. Rescreening should occur no less than 5 days after the last Screening Visit.

4.5 Withdrawal Criteria

A distinction must be made between patients who discontinue study treatment prematurely and patients who are discontinued from the study.

In all cases of impending premature study treatment discontinuation or patient requests for withdrawal from study visits, the Investigators should discuss with the patient his/her options for continuing in the study. The Investigator should ensure he/she understands the reasons for a patient's desire to discontinue study treatment or withdraw from the study prior to completion and document these reasons in the electronic case report form (eCRF).

4.5.1 Discontinuation of Study Treatment

A patient may be discontinued from study treatment before the end of the Treatment Period but remain in the study for safety follow-up for any of the following reasons:

- A confirmed complete response (CR) is attained, and the patient has been treated for at least 8 cycles (ie, at least 24 weeks), including 2 cycles of the combination treatment (including 2 doses of pembrolizumab) from the date when the initial CR was declared;
- Occurrence of a severe systemic hypersensitivity reaction that is uncontrolled with standard management or requires high dose steroids;
- Occurrence of necrosis, ulcerations, bleeding, or any other serious complication in healthy tissues surrounding the injected tumor;
- Occurrence of injected tumor ulcerations that do not show a healing trend in a 3-week period;
- Occurrence of any other medical condition or circumstance that exposes the patient to substantial risk and/or does not allow the patient to adhere to the requirements of the protocol;
- Any SAE, clinically significant AE, severe laboratory abnormality, intercurrent illness, or other medical condition which indicates to the Investigator that continued participation is not in the best interest of the patient;

- Pregnancy;
- Requirement of prohibited concomitant medication;
- Patient requests discontinuation of study treatment for any reason; and/or
- Patient failure to comply with protocol requirements or study-related procedures.

If a patient discontinues CyPep-1 but remains eligible to participate in the study after review by the Investigator and Medical Monitor, pembrolizumab treatment will be continued Q6W as per institutional guidelines until PD, unacceptable toxicity, or consent withdrawal by patient for a maximum of 18 treatment cycles. All assessments will continue to be performed according to the Schedule of Assessments (Appendix A).

If a patient discontinues pembrolizumab but remains eligible to participate in the study after review by the Investigator and Medical Monitor, CyPep-1 treatment will be continued Q2W until PD, unacceptable toxicity, or consent withdrawal by patient for a maximum of 18 treatment cycles. All assessments will continue to be performed according to the Schedule of Assessments (Appendix A).

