3.1.1.1 Dose-limiting toxicities

All toxicities will be graded using National Cancer Institute (NCI) Common Terminology Criteria for Adverse Events (CTCAE) v5.0 based on the Investigator assessment.

The DLT window of observation will be during Cycle 1 (initial 6 weeks of study treatment).

The occurrence of any of the following toxicities during Cycle 1 will be considered a DLT, if assessed by the Investigator to be possibly, probably, or definitely related to study treatment administration:

- 1. Grade 4 non-hematologic toxicity (not laboratory);
- 2. Grade 4 hematologic toxicity lasting ≥7 days, except thrombocytopenia:
 - o Grade 4 thrombocytopenia of any duration; or
 - o Grade 3 thrombocytopenia associated with clinically significant bleeding.
- 3. Any non-hematologic AE ≥Grade 3 in severity should be considered a DLT, with the following exceptions:
 - o Grade 3 fatigue lasting ≤3 days;
 - o Grade 3 diarrhea, nausea, or vomiting unless it persists for >3 days despite the use of anti-emetics or anti-diarrheals per standard of care; or
 - o Grade 3 rash without use of corticosteroids or anti-inflammatory agents per standard of care.
- 4. Any Grade 3 or Grade 4 non-hematologic laboratory value if:
 - o Clinically significant medical intervention is required to treat the patient;
 - o The abnormality leads to hospitalization;
 - o The abnormality persists for >1 week; or

- The abnormality results in a drug-induced liver injury.
- Exceptions: Clinically non-significant, treatable, or reversible laboratory abnormalities including liver function tests, uric acid, etc. Isolated laboratory abnormalities ≥Grade 3 (not present at baseline) that resolve to <Grade 1 in <3 days without clinical sequelae or need for therapeutic intervention.

- 5. Febrile neutropenia Grade 3 or Grade 4:
 - o Grade 3 is defined as absolute neutrophil count (ANC) <1000/mm³ with a single temperature of >38.3°C (101°F) or a sustained temperature of ≥38°C (100.4°F) for more than 1 hour; or
 - o Grade 4 is defined as ANC <1000/mm³ with a single temperature of >38.3°C (101°F) or a sustained temperature of ≥38°C (100.4°F) for more than 1 hour with life-threatening consequences and urgent intervention indicated.
- 6. Prolonged delay (>2 weeks) in initiating Cycle 2 due to treatment-related toxicity;
- 7. Delay in administration of CyPep-1 for >7 days;

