3.1.2 Phase 2a

The Phase 2a portion of the study will comprise of all approximately 90 patients (including the first 6 patients assessed in the Phase 1b portion) to assess the efficacy, safety, and pharmacodynamics of CyPep-1 (20 mg Q2W) in combination with the anti-PD-1 antibody pembrolizumab (400 mg Q6W). Patients will receive IT injections of a fixed concentration of CyPep-1 Q2W beginning at Cycle 1 Visit 1. Pembrolizumab will be administered IV at a fixed dose Q6W beginning at Cycle 1 Visit 1. Each treatment cycle will be 6 weeks, and treatment will continue for a maximum of 18 cycles (108 weeks) or until the occurrence of confirmed progressive disease (PD), excessive toxicity, death, or withdrawal of consent. Patients who complete all 18 cycles, which is the Food and Drug Administration (FDA)-approved maximum duration of pembrolizumab use, may continue receiving CyPep-1 at the current dose if determined beneficial by the Investigator and following approval of the Sponsor. CyPep-1 monotherapy may proceed until the occurrence of confirmed PD, excessive toxicity, death, or withdrawal of consent.

Radiological assessments and local measurements of tumor lesion(s), according to RECIST v1.1, will be conducted and evaluated at baseline (screening) and at 8-week intervals after the first dose of CyPep-1 through the last Progression Follow-up Visit during the Follow-up Period (up to approximately 26 months after the start of treatment). Radiological assessments can be more frequent if clinically indicated. Magnetic resonance imaging (MRI) or computed tomography (CT)

are the preferred scanning procedures to be used in this study. Selection of either MRI or CT should be based on individual patient considerations and local regulations and is at the Investigator's discretion. Once selected for each patient, the same scanning procedure should be used consistently at all remaining visits. Scans will be collected and held centrally for potential central radiologic review. When radiological PD is identified by the Investigator, PD is to be confirmed by another set of scans performed approximately 4 weeks to ≤8 weeks later according to immune-RECIST (iRECIST) guidelines (Appendix D). If PD is not confirmed, study treatment will continue until progression is confirmed.

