5.5.3.2 Pembrolizumab administration

The dose of pembrolizumab in combination with CyPep-1 will be 400 mg Q6W administered via a 30-minute infusion, beginning at Cycle 1 Visit 1. On the visits that CyPep-1 and pembrolizumab are administered on the same day, CyPep-1 is to be administered 30 to 60 minutes **after** pembrolizumab infusion is completed. Pembrolizumab may be administered up to 3 days before or after the scheduled Visit 1 of each cycle from Cycle 2 onward.

Every effort should be made to ensure the duration of infusion administration will be as close to 30 minutes as possible. However, given the variability of infusion pumps from study site to study

site, a window between -5 and +10 minutes is permitted (ie, the infusion time is $30 \left[-5/+10 \right]$ minutes).

The Pharmacy Manual contains specific instructions for the preparation of the pembrolizumab infusion and administration of infusion solution.

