7.2 Radiological Assessment

A baseline radiology assessment will be performed within 4 weeks prior to Cycle 1 Visit 1 to identify injected lesions and non-injected lesions and these lesions will be assessed according to RECIST v1.1. Subsequent radiological assessments will be performed Q8W (±3 days) after the first dose of CyPep-1, according to RECIST v1.1, until the occurrence of confirmed PD as defined by iRECIST (Appendix D), start of a new anti-cancer treatment, pregnancy, death, withdrawal of consent, or end of study (approximately 26 months after the start of treatment). Tumor scans may be performed more frequently if clinically indicated. MRI or CT are the preferred scanning procedures to be used in this study. Selection of either MRI or CT should be based on individual patient considerations and local regulations and is at the Investigator's discretion. Once selected for each patient, the same scanning procedure should be used consistently at all remaining visits. Scans will be collected and held centrally for potential central radiologic review.

Scan timing should follow calendar days and should not be adjusted for delays in cycle starts.

A confirmatory radiological assessment is required 4 weeks after an initial radiological scan leading to an assessment of PD. If the PD is confirmed, the initial assessment of PD will be considered as the "first documented PD." If PD is not confirmed, the first measured PD will be disregarded and assessments should continue as per protocol (ie, the next radiological assessment will be performed after an 8-week interval).

If a patient discontinues study treatment without documented disease progression, every effort should be made to monitor disease status by continuing tumor scans Q8W from start of study treatment. Scans will be continued until occurrence of confirmed PD as defined by iRECIST (Appendix D), start of a new anti-cancer treatment, pregnancy, death, withdrawal of consent, or end of study (approximately 26 months after the start of treatment).

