1 INTRODUCTION

The purpose of this Statistical Analysis Plan (SAP) is to provide a description of the statistical methods to be implemented for the analysis of data from the study with protocol number CYP003 for Phase 1b only. Due to the termination after Phase 1b of the study, this SAP will contain a full report on safety endpoints and an abbreviated selection of efficacy endpoints. The SAP will be finalized prior to database lock. Any deviations from the SAP after database lock will be documented in the final Clinical Study Report (CSR).

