3.4 Efficacy Assessment

All efficacy analysis will be based on the Full Analyses Set (FAS).

The Investigator will assess tumor responses according to Response Evaluation Criteria in Solid Tumors (RECIST) 1.1 criteria, immune Response Evaluation Criteria in Solid Tumors (iRECIST) criteria and Intratumoral-Response Evaluation Criteria in Solid Tumors (itRECIST); see Appendices B, C, and D respectively. Efficacy evaluations will include the following: Local measurement of tumor lesions, radiological assessments, tumor biopsy, and peripheral cytokines.

Response (Complete response [CR] / partial response [PR], immune complete response [iCR] / immune partial response [iPR]) must be confirmed by a repeat assessment performed no less than 6 weeks after the criteria for response are first met. When stable disease (SD) or immune stable disease (iSD) is believed to be the best response, it must also meet the minimum interval of 6 weeks (42 days) from the start of the treatment. Best overall response (BOR) will be determined based on the overall visit responses from each RECIST and iRECIST assessment by the Investigator. BOR is defined as the best response designation (in the order of CR, PR, SD, progression of disease [PD] using RECIST, and in the order of immune complete response [iCR], immune partial response [iPR], immune stable disease [iSD], immune confirmed progression of disease [iCPD] and immune unconfirmed progression of disease [iUPD] using iRECIST) a patient has had following the first dose of study treatment, but prior to and including progression (PD for RECIST and iCPD for iRECIST) or the last evaluable assessment in the absence of disease progression. Patients with no evaluable assessments after the first study dose will be assigned to

the not evaluable (NE) category. The determination of the best overall response by RECIST 1.1, iRECIST and itRECIST is summarized in Appendices B, C, and D.

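### The complete-response stopping rule equates 8 cycles with 24 weeks, but at 6 weeks per cycle 8 cycles is 48 weeks, so the earliest stop for an early complete responder is uncertain by up to 24 weeks

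*Protocol*

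**What the plan says.** Protocol Section 4.5.1 lists reasons for which a patient may come off study treatment before the end of the Treatment Period. The first is a confirmed CR, provided that "the patient has been treated for at least 8 cycles (ie, at least 24 weeks"). The same bullet then adds a second condition on treatment given after the response: "including 2 cycles of the combination treatment (including 2 doses of pembrolizumab) from the date when the initial CR was declared".

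The cycle length is fixed elsewhere:

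- Protocol Section 3.1.2, and the Synopsis in the same terms: "Each treatment cycle will be 6 weeks, and treatment will continue for a maximum of 18 cycles (108 weeks").
- Protocol Section 3.1.1.1: "The DLT window of observation will be during Cycle 1 (initial 6 weeks of study treatment").
- Protocol Section 5.5.3.2: "The dose of pembrolizumab in combination with CyPep-1 will be 400 mg Q6W administered via a 30-minute infusion, beginning at Cycle 1 Visit 1".
- SAP Section 3.3.9 adds 42 days (6 weeks) to the last pembrolizumab dose when computing treatment duration.

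Two further provisions bear on timing. Protocol Section 7.2: "Subsequent radiological assessments will be performed Q8W (±3 days) after the first dose of CyPep-1". SAP Section 3.4 says that a response "must be confirmed by a repeat assessment performed no less than 6 weeks after the criteria for response are first met".

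**The concern.** The rule states its minimum twice, in cycles and in weeks, and presents the two as equivalent. With 6-week cycles they are not. A stop at week 30, for example, satisfies the week count and fails the cycle count.

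This is an operative threshold for ending treatment. For a patient with an early CR, the reading chosen decides how much more of both drugs is given, including an antibody whose immune-related toxicity Section 5.5.3.3 manages at length. It also bears on reporting. The SAP summarises reasons for treatment discontinuation (3.3.1), protocol deviations (3.3.2), and treatment duration and cycles initiated (3.3.9). Whether a CR-based stop between weeks 24 and 48 complied with the protocol depends on which figure is used.

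**Working it through.** **Cycle arithmetic.** Weeks = cycles × weeks per cycle.

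- Check on the protocol's own maximum: 18 × 6 = 108 weeks. This reproduces Section 3.1.2.
- The CR rule: 8 × 6 = 48 weeks, not 24.
- The other way round: 24 / 6 = 4 cycles.
- To make 8 cycles equal 24 weeks, a cycle would have to last 24 / 8 = 3 weeks. Neither document defines such a cycle. Counting by the 2-week CyPep-1 interval gives 8 × 2 = 16 weeks, which does not match either.

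**Earliest stop.** The second condition of the rule requires 2 cycles after the initial CR: 2 × 6 = 12 weeks. Any 12-week span starting at the CR contains two scheduled 6-weekly infusions, so the two-dose requirement adds nothing. Confirmation does not bind either: the SAP asks for at least 6 weeks, the next 8-weekly scan falls at CR + 8, and that precedes CR + 12. With M the minimum duration (24 or 48):

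earliest stop week = max(M, CR week + 12)

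The doses in the gap are those scheduled from the earlier stop week up to, but not including, the later one. Pembrolizumab is scheduled at weeks 0, 6, 12 and so on, and CyPep-1 at weeks 0, 2, 4 and so on. Visit windows are ignored.

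| Initial CR at scan (week) | CR + 12 | Stop, M = 24 | Stop, M = 48 | Gap (weeks) | Pembrolizumab doses in gap | CyPep-1 days in gap |
|---|---|---|---|---|---|---|
| 8 | 20 | 24 | 48 | 24 | 4 | 12 |
| 16 | 28 | 28 | 48 | 20 | 3 | 10 |
| 24 | 36 | 36 | 48 | 12 | 2 | 6 |
| 32 | 44 | 44 | 48 | 4 | 0 | 2 |
| 40 | 52 | 52 | 52 | 0 | 0 | 0 |

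**Alternative count.** If the 2 post-CR cycles must be whole cycles on the 6-week grid, CR + 12 is replaced by 6 × ceil(CR week / 6) + 12, which gives 24, 30, 36, 48 and 54. The gaps become 24, 18, 12, 0 and 0 weeks. The maximum is unchanged. Only the week-16 entry (18 weeks, 3 infusions, 9 CyPep-1 days) and the week-32 entry (no gap) move.

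**The case against.** The strongest reply concedes the arithmetic and disputes the consequence.

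- **Neither figure is a hard floor.** The CR criterion is one of ten alternative reasons in Section 4.5.1, and the same list allows a stop at the patient's request or on the investigator's judgment. This stands. The ambiguity concerns only an elective stop under the CR criterion.
- **A cautious site can satisfy both figures.** Both are minimums, and a patient treated for 48 weeks meets each. The cycle count comes first, and the second condition is also counted in cycles, so 8 cycles is a natural default. That is a fair guess at intent, but the text gives the week count as an exact restatement and does not say that cycles prevail.
- **The dose counts are schedule maxima.** They assume that every planned dose is given, and CyPep-1 needs a lesion to inject. The Synopsis treats a complete response in a lesion as a reason to move on from it, so 12 further injection days may not be deliverable after a CR. This stands too, although the rule itself expects combination cycles after CR.
- **Nothing inferential depends on it.** Scans continue every 8 weeks after treatment stops, and the threshold enters no SAP endpoint, the sample size or the response-rate decision rule. The SAP opens with "Due to the termination after Phase 1b of the study", a part planned for 6 patients, and neither document reports a CR. This stands and limits the importance of the point.
- **The Appendix A schedule is missing from the text available for this review.** It therefore cannot be ruled out that it bears on the question.

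**Conclusion.** The rule is wrong as written. Eight 6-week cycles last 48 weeks, twice the 24 weeks stated, and no text available for this review settles which minimum applies. The earliest CR-based stop is uncertain by up to 24 weeks. That maximum is reached by a CR at the first scheduled scan, with at most 4 pembrolizumab infusions and 12 CyPep-1 injection days depending on the reading. The gap falls as the CR comes later. It closes at a CR at week 32 if whole cycles are counted, and at week 40 otherwise.

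These sizes assume CR declared at the scheduled 8-weekly scans, 6-week cycles without delay, and every scheduled dose given. Practical impact is low, because few patients could be affected after termination at Phase 1b, and possibly none. The number still deserves correction because it sits in a treatment-stopping criterion and not in background text. A 3-week cycle carried over from another regimen would explain the figure, but the documents do not say so.

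**What to change.** State one duration in Protocol Section 4.5.1: either at least 8 cycles (48 weeks) or at least 4 cycles (24 weeks), whichever the sponsor intends. It would also help to say whether the 2 post-CR cycles run from the CR date or are counted as whole cycles.

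If no patient can still be affected, an amendment is unnecessary. The CSR should then state which reading was applied to any patient who stopped for confirmed CR, or that there was none. The cost is one corrected line or one sentence, and no analysis changes. Any later protocol that reuses this text should carry the corrected figure.
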